7.1 Follow-up Mammograms

Patients will have the first follow-up bilateral mammogram at 6 months (+/- 3 months) following the completion of their radiation therapy and then bilateral mammograms yearly. Breast MRI can be substituted for one of the bilateral mammograms. This decision will be made at the discretion of the treating physician.

Data Submission: Forms should be submitted to QACT at the Dana Farber Cancer Institute in compliance with the Data Submission schedule below.

- The original forms must be mailed to the QACT

| Form | | Submission Schedule |
|------|-----------------------|---|
| | On-Study Form | Within 14 days of patient entry |
| | During Treatment | After completion of therapy |
| | Cosmetic Outcome | 
 • Baseline (pre-treatment or within treatment period) • 3-4 weeks post treatment (not mandated) • First evaluation (within 3-9 wks) after treatment • q 6 months for 5 years and q 1 yr for 10 years after treatment |
| | Radiation Data | 
 • RT 1 Form at completion of Simulation • RT 2 and RT3 (Radiation, Physics and Dosimetry) Forms at completion of therapy • DVH graph to PI¹ |
| | F/U Data ² | 
 • Every 6 mos yr 2-5 • Yearly after year 5 |

1.DVH (dose-volume histogram) graph should include DVH for lungs, heart, GTV, PTV, and non-target breast tissue (whole breast minus PTV) and whole breast (see forms RT3 or Dosimetry form).

2. The Mammography form should be submitted every 6 months to capture the results from each mammogram for the first 5 years then yearly after that.

8.0 Modality Review/Quality Assurance and Documentation:

- The treatment plan will be approved prior to the start of radiation therapy by the site-specific PI ([name] for MGH and BMC, [name] for BIDMC, or [name] for BWH/DFCI).
- Submit copies of the following to the site PI ([name], PhD, at MGH or [name], at BIDMC) upon completion of treatment to

[name], PhD, Department of Radiation Oncology, Massachusetts General Hospital [name]. [contact] [contact] email: [contact]

[name], Department of Radiation Oncology, Beth Israel Deaconess Medical Center, Department of Radiation Oncology, [name].
[contact] [contact] email: [contact]

- Final approved RT plan (including axial, sagittal and coronal cuts at the isocenter), also dose-volume histograms of the target volume, ipsilateral and contralateral lungs, heart (for both sides), PTV,

GTV (seroma), and non-target breast tissue (breast minus PTV), whole breast. (**A copy of these records should also be sent to the overall PI [name], MD, PhD at MGH*).

- Radiotherapy Initial Report Form (RT-1).
- Radiotherapy Total Dose Record (RT-2).
- Radiotherapy Physics/Dosimetry Record (RT-3).
- Treatment record (show daily doses).
- Note: If Polaroid or other photographic process for the duplication of localization and verification films is employed, ensure that these images are of sufficiently good quality for review. Photograph these films at a sufficiently close distance to ensure that the portal (or verification) film fills the entire Polaroid print.
- Direct questions regarding dose calculations or documentation to: [name] [name] [contact] or [name] [contact].
- Direct questions regarding the radiotherapy section of this protocol to: [name] [name] [contact] or [name] [contact].

9.0 Dose Modifications And Management of Toxicity

9.1 Hypersensitivity Reactions: Radiotherapy is given in continuous course. It is not anticipated that treatment breaks to the breast should be needed. If a break seems necessary the situation should be discussed with [name] or [name].

9.2 If a break must be given due to unavoidable medical necessity (i.e., concurrent illness), please discuss with [name] or [name].

9.3 Anticipated Toxicity and Adverse Reactions: Erythema and dry desquamation in the radiation fields are anticipated to occur commonly. Some patients may develop moist desquamation, which usually heals within a few weeks. Cellulitis is rare. Appropriate nursing care for this should be given according to standard practices. Should a prolonged treatment break seem necessary (refer above), the situation should be discussed with [name] or [name]. Some patients may have mild tenderness in the treated area.

10.0 Accrual Goal and Statistical Power:

The primary objective of this study remains to determine if accelerated partial breast irradiation is feasible in this patient group. However, this feasibility will now be determined based on events occurring to the patient within 1 year of registration, rather than within 3 years. (See the Introduction for justification of this decision.) The design is also being changed to include accrual at three dose-levels (32 Gy, 36 Gy, and 40 Gy). In addition, accrual used to be 40 patients per year, but since APBI has been widely-publicized, the accrual rate became around 40-50 patient per year in this last year and is expected to increase possibly more than 50 patients per year when the consensus statement is published.

The original statistical design of this study was based on a single radiation dose, using a two-stage design, with a maximum of 34 patients to be entered on the first stage and a maximum of 66 patients on the second stage. There was no pause after the first stage of accrual, but the study was to be stopped at any time that 5 patients of the first 34 entered were noted to have a bad event (defined below) or at any time that 9 patients (entered in

either stage) had been noted to have a bad event. Using this design, there was a 59% chance of terminating accrual during the first stage if the true rate of a bad event is 15% and a 9% chance if the true rate of a bad event is 7%. There was a 5% chance of deeming the treatment feasible if the true rate of a bad event is 15% and an 80% chance if the true rate of a bad event is 7%. We have not yet had 34 patients followed for at least 1 year on the first dose (this will occur in July 2005), and at this early time there is no reason to think that the 32 Gy dose is associated with unacceptable toxicity.

A dose level will be deemed infeasible if too many patients have at least one of the following outcomes:

- a) The patient has a breast cancer recurrence (local, regional, or distant) within 1 year of protocol registration (since this will necessitate her removal from study, see section 5.1.4).
- b) The patient dies from causes judged to be related to her treatment within 1 year of protocol registration.
- c) The patient develops fat necrosis or other grade 4 skin or grade 4 subcutaneous toxicity or requires surgery for her skin or subcutaneous toxicity within 1 year of protocol registration.

In the rest of this section, a patient who has at least one of these 4 outcomes is said to have “a bad event.”

We will continue to use a two-stage design for each of the three dose-levels. With the increased accrual rate, at the time the decision has to be made on whether to increase the dose level, there will be 50 patients who have been followed for at least 1 year. We have therefore changed the size of the first stage of accrual to 50 patients (and made the size of the second stage 50 patients, in order to keep the maximum number of patients at each dose-level at 100).

Since the decision to increase the dose will be based on the results in the first 50 patients, and since higher doses might have higher toxicity rates, we have also changed the probabilities of the null and alternative hypotheses for the first two doses to 13% and 5%, respectively. For the third and final dose-level, the null and alternative hypotheses are unchanged at 15% and 7%, respectively.

Even the one-year period needed to observe the patient for fat necrosis or other grade 4 skin or grade 4 subcutaneous toxicity remains too long to pause accrual after the first stage of a two-stage design. However, we will continue to keep the provision to stop the study as soon as an unacceptable number of patients with a bad event have been observed. In addition, if at any time (during either its first or second stage of accrual) the toxicity rate at a dose is found to be unacceptable (based on follow-up of 1 year or longer), accrual to any higher dose will also terminate.

For each of the first two dose levels (32 Gy and 36 Gy), accrual will be terminated at any time there has been 5 patients with a bad event among the 50 patients entered on the first stage of each dose level. For the second stage of each of these dose levels (that is, after the first 50 patients have been accrued), accrual will be terminated at any time that there have been a total of 8 patients with a bad event on this dose. With this design, there is an 80% chance of terminating accrual to this dose (and the entire protocol) early if the true probability of a bad event with this dose is 13%, and a 10% chance if the true probability of a bad event on this dose is 5%. There is a 4% chance of deeming the dose level feasible if the true probability of a bad event on this dose is 13%, and an 83% chance if the true probability of a bad event on this dose is 5%.

For the third (and final) dose level, accrual will be terminated at any time there has been 6 patients with a bad event among the 50 patients accrued during its first stage. During the second stage, accrual will be terminated at any time there have been a total of 9 patients with a bad event on this dose. With this design, there is a 64% chance of terminating accrual early on this dose if the true probability of a bad event on this dose is 15%, and a 6% chance if the true probability of a bad event on this dose is 7%. There is a 5% chance of deeming this dose level feasible if the true probability of a bad event on this dose is 15%, and an 82% chance if the true probability of a bad event on this dose is 7%.

There could be an interim analysis of the events when the first 50 patients for each dose level (the 36 and 40 Gy) have been followed for at least 1 year.

At this time, the number of patients in the third cohort will be increased from 100 to 200 patients. All patients in this cohort will be treated with the same dose as the third cohort (40 Gy). For analyzing our endpoints, all patients in the third cohort will be combined (for a total of 200 patients). Our primary endpoint for this expanded cohort will be limited to fat necrosis requiring surgery within 3 years of protocol registration.

We expect that 90% of the 200 patients will be available for assessing fat necrosis for 3 years after registration (with the remaining 10% having a recurrence, developing metastases, dying, or being lost to follow-up before the end of 3 years). If more than 5% of the 180 patients (i.e., more than 9 patients) have fat necrosis requiring surgery by 3 years after registration, then the dose of 40 Gy will be considered too toxic. Using this design, if the true probability of this toxicity is 3%, then there will be a 0.05 chance of declaring this dose too toxic; if the true probability of this toxicity is 9% then there will be a 0.97 chance of declaring this dose too toxic.

If none of the 180 patients have this toxicity, the 95% confidence interval (CI) for the probability of fat necrosis requiring surgery will be 0 to 1.7%; if 9 of the 180 patients have this toxicity, a 95% CI will be 2.3 to 9.3%.

The old stopping rule (based on bad events occurring within the first year after registration) will still be in force for the third cohort (these patients have not all yet been followed for a year). That is, all accrual to this protocol will end if 6 or more of the first 50 patients in the third cohort have a "bad event" within a year of protocol registration or if 9 or more of the 100 patients in the third cohort have a "bad event" within a year of protocol registration.

There could be a first interim analysis of the events when the first 50 patients for the 40 Gy dose level have been followed for at least 1 year. Other analysis can follow if the information is deemed by the PI as worthwhile to be published.

11.0 Accrual Rate:

This study has been designated by the Dana Farber/Harvard Cancer Center (DF/HCC) as a rapidly accruing study. We expect an average of 40-50 patients per year to enter this study. If accrual in any 12-month period drops below 20 patients, we will consider terminating the study for lack of accrual.

References

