2.0 Objectives

2.1 Primary Objective

To evaluate the feasibility of PBI directed XRT in selected stages 0 and I female breast cancer patients within each dose level. The study will be deemed infeasible if the total percent of patients who have at least one of the following outcomes is large:

- a) Within 1 year of protocol registration, the patient develops histological fat necrosis or other grade 4 skin or grade 4 subcutaneous toxicity, or requires surgery for her skin or subcutaneous toxicity
- b) Within 1 year of protocol registration, the patient develops any breast cancer recurrence or for any reason has additional ipsilateral breast surgery or other ipsilateral breast treatment
- c) Within 1 year of protocol registration, the patient dies from causes judged to be related to her treatment.
- d) Within 3 years of protocol registration, the patient treated with 40 Gy develops fat necrosis requiring surgery.

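### The one-year feasibility objective in Section 2.1 counts ipsilateral surgery or treatment for any reason; the event counted by the Section 10.0 boundaries leaves it out, and the two lists need reconciling, chiefly for 32 and 36 Gy

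*Combined protocol and SAP*

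**What the plan says.** Section 2.1 states the primary objective as feasibility, judged dose by dose: "The study will be deemed infeasible if the total percent of patients who have at least one of the following outcomes is large". Item (b) of its list covers any recurrence within 1 year and also a patient who "for any reason has additional ipsilateral breast surgery or other ipsilateral breast treatment". The section gives no number for what counts as large.

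Section 10.0 gives its own list and its own consequence: "A dose level will be deemed infeasible if too many patients have at least one of the following outcomes". The list has three lettered items, all within 1 year:

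- (a) breast cancer recurrence;
- (b) death judged related to treatment;
- (c) "The patient develops fat necrosis or other grade 4 skin or grade 4 subcutaneous toxicity or requires surgery" for skin or subcutaneous toxicity.

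The section then says that "a patient who has at least one of these 4 outcomes is said to have" a bad event, and confines that term to the rest of the section. The one-year limits count this event: 5 of the first 50 and 8 in total at 32 and 36 Gy, and 6 of the first 50 and 9 in total at 40 Gy.

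For the enlarged 40 Gy cohort, Section 10.0 makes fat necrosis requiring surgery within 3 years the primary endpoint. It adds: "The old stopping rule (based on bad events occurring within the first year after registration) will still be in force for the third cohort". The revision log records permanent closure to accrual in October 2010, with analysis to proceed on 330 patients.

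**The concern.** Each section says that its own list decides infeasibility, and the lists differ. A patient who has ipsilateral breast surgery within the year for a reason other than recurrence or skin or subcutaneous toxicity, such as a benign finding, fails under Section 2.1 but adds nothing to the count in Section 10.0. The stated objective is therefore wider than the rule that judges it.

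Section 10.0 does not present this as a deliberate narrowing. It says that the primary objective remains feasibility and names what is changing: the time window ("this feasibility will now be determined based on events occurring to the patient within 1 year of registration") and the number of dose levels. It does not mention taking any-reason surgery or treatment out of the event.

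At stake is what the word feasible means in the report for 32 and 36 Gy. The limits are small counts, so a few patients classified differently can move a dose level from pass to fail.

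**Working it through.** **1. The two one-year lists side by side.**

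| Outcome within 1 year | Section 2.1 | Section 10.0 |
|---|---|---|
| Recurrence | yes (b) | yes (a) |
| Treatment-related death | yes (c) | yes (b) |
| Grade 4 skin or subcutaneous toxicity, or surgery for it | yes (a) | yes (c) |
| Fat necrosis | yes, if histological (a) | yes, not so qualified (c) |
| Other ipsilateral surgery or treatment, any reason | yes (b) | **no** |

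The fat necrosis row is a small wording difference, partly closed because Appendix 2 grades subcutaneous necrosis as grade 4. The last row is the substantive gap.

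**2. Reproducing the plan's figures at 32 and 36 Gy.** Let X1 and X2 be the bad events in the first and second 50 patients, each binomial with rate p, all evaluable at 1 year. The dose passes if X1 ≤ 4 and X1 + X2 ≤ 7:

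P(feasible) = Σ over x = 0 to 4 of P(X1 = x) × P(X2 ≤ 7 − x).

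At p = 5%: 0.0767 + 0.2001 + 0.2512 + 0.1971 + 0.1034 = 0.8285 (plan: 83%). At p = 13%: 0.0365 (plan: 4%). First-stage stopping, P(X1 ≥ 5), is 0.104 at 5% and 0.796 at 13% (plan: 10% and 80%). All four figures reproduce.

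**3. Effect of counting the Section 2.1 list against the same limits.** Assume that patients who fail only under 2.1(b) add q to the 5% rate. They do not overlap the bad event by definition, so the rates add. In 100 patients, one point is one expected patient.

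| q | Rate counted | P(feasible) |
|---|---|---|
| 0 | 5% | 0.829 |
| 1 point | 6% | 0.696 |
| 2 points | 7% | 0.546 |
| 3 points | 8% | 0.401 |

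In the other direction, suppose the Section 2.1 rate is the unacceptable 13% and q of it goes uncounted. The chance of passing rises from 4% to 7%, 11% or 18% for q of 1, 2 or 3 points.

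**4. One patient at the final limit.** Both escalations have taken place (Section 1.3), so the first-stage decision is past. One extra patient reverses a pass only if the total is exactly 7:

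Σ over x = 0 to 4 of P(X1 = x) × P(X2 = 7 − x) = 0.083 at p = 5%, and 0.083 / 0.829 = 0.10.

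Allowing also for such a patient to trip the first-stage limit, with an even chance of being in either stage, would give 0.083 + 0.5 × 0.073 = 0.120, or 14% of passes. That includes a decision no longer open, so 10% is the relevant figure.

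**5. 40 Gy.** No series is given. The one-year count there is kept as an accrual rule, and the printed limits of 6 and 9 give 71% feasible at a 7% rate, not the printed 82%. That mismatch is a separate matter.

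**The case against.** The strongest reply is that Section 10.0 plainly governs. Section 2.1 has no threshold and cannot yield a verdict alone. Section 10.0 is the statistical section, names its event, and ties every one-year limit and probability to it; Section 1.3 sends the reader there for details. This largely stands: there is one executable rule, and a reader would naturally follow it. It does not close the gap. No sentence gives precedence, the definition is confined to its own section, and if Section 10.0 is meant to govern, Section 2.1 misstates the primary endpoint.

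The second reply is that the extra event may never occur. Recurrence and surgery for skin or subcutaneous toxicity count under both lists, and the 2 mm margin requirement in Section 3.1.1 may reduce later re-excision. This stands in full: the added points are assumptions, and with none of these patients nothing changes.

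The third reply concerns 40 Gy, and it also stands. The expanded cohort's primary endpoint is limited to the 3-year outcome, and the one-year count survives there as a rule for ending accrual that has already closed.

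A reader might infer from the count of four that the any-reason item was dropped by accident. The documents do not show this. The number may be a slip or a different way of counting the parts of item (c).

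**Conclusion.** The two lists conflict, and the conflict concerns the definition of the primary feasibility event. It is a wording fault of minor to moderate weight. No printed probability is wrong because of it.

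Its practical reach is mainly the one-year conclusion at 32 and 36 Gy. If patients failing only under 2.1(b) add 1 to 3 points to a 5% rate, the chance of calling the dose feasible falls from 83% to between 70% and 40%. One such patient would overturn about 10% of passing verdicts at the final limit. Both figures assume a 5% base rate, 100 evaluable patients and unchanged limits; the added rate is unknown and may be zero.

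Two stronger readings go too far. The plan does not lack a usable rule, since Section 10.0 supplies one. Nor do the documents show that an escalation decision or the 40 Gy conclusion was affected: they report no patient of this kind, and the 40 Gy primary endpoint does not depend on the one-year list.

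**What to change.** Give Sections 2.1 and 10.0 the same one-year definition, word for word, and state that this is the event the limits count. The definition should say whether ipsilateral surgery or treatment for any reason is included and, if so, whether a biopsy counts; Appendix 2 notes that one may be needed to tell fat necrosis from recurrence. It should also say whether fat necrosis must be histological. Correct or explain the count of four. Set item 2.1(d) apart as the 3-year endpoint for 40 Gy.

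In the final report, name the definition behind each feasibility conclusion. Tabulate the counts under the other definition at 32 and 36 Gy, and descriptively at 40 Gy.

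The cost is a text change and one table, with no new patients or visits. The table should carry a note that any-reason surgery may be incompletely captured: Section 6.2.2 asks for reports of fat necrosis or other complications requiring surgery, which is narrower, and the data forms are not available to check.

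### The error rates quoted for the 40 Gy stopping rule belong to a different rule: with the written counts (6 of 50, 9 in total), the chance of passing an acceptable dose is about 71%, not 82%

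*Combined protocol and SAP*

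**What the plan says.** All of this is in Section 10.0 (Accrual Goal and Statistical Power) of the combined protocol and SAP.

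- **Stage sizes and hypotheses.** Each dose level has two stages of 50 patients. At 40 Gy the null and alternative bad-event rates are 15% and 7%.
- **Rule at 40 Gy.** The first-stage trigger for stopping is met when "there has been 6 patients with a bad event among the 50 patients accrued during its first stage". The trigger that applies after those patients are in is met when "there have been a total of 9 patients with a bad event on this dose".
- **Stated performance at 40 Gy.** At a true rate of 15%, "there is a 64% chance of terminating accrual early on this dose"; at 7% the chance is 6%. The dose is deemed feasible with probability 5% at a true rate of 15% and 82% at 7%.
- **Restatement.** When the third cohort is enlarged to 200, the one-year rule is kept in force. Its first condition for closing the whole protocol to accrual reads "if 6 or more of the first 50 patients in the third cohort have a", and its second condition reads "if 9 or more of the 100 patients in the third cohort have a". Both refer to bad events in the first year after registration.
- **Comparison rule at 32 and 36 Gy.** Accrual stops at 5 of the first 50 or at 8 in total. The stated early-termination chances are 80% (true rate 13%) and 10% (true rate 5%), and the stated chances of being deemed feasible are 4% and 83%.

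**The concern.** The counts and the percentages at 40 Gy cannot both be right. Six events in 50 patients is 12%, below the 15% null rate, so a rule that stops there should trigger in well over 64% of trials when the true rate is 15%. The restatement says 6 or more and 9 or more, so the counts cannot be read as the largest acceptable numbers.

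The percentages are the error rates of the one-year feasibility decision at the final dose, which Section 2.1 makes part of the primary objective within each dose level. A reader relying on them would believe that an acceptable dose has an 82% chance of passing. The choice of rule can also change the verdict. With exactly 6 events in the first 50 patients, the written rule ends accrual and the rule behind the percentages does not. With 9 events among 100, of which at most 6 fell in the first 50, the written rule fails the dose and the other passes it.

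**Working it through.** **Inputs, all from Section 10.0.** Stage sizes n1 = n2 = 50. Stopping counts r1 (first stage) and r (total): 5 and 8 at 32 and 36 Gy; 6 and 9 at 40 Gy. True rates p: 13% and 5% at the first two levels; 15% and 7% at 40 Gy.

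**Formulas.** Let X1 and X2 be independent Binomial(50, p) counts of bad events in the two stages.

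- P(early termination) = P(X1 ≥ r1)
- P(feasible) = Σ over x = 0, …, r1 − 1 of P(X1 = x) × P(X2 ≤ r − 1 − x)

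**Step 1: reproduce the plan's own figures at 32 and 36 Gy (r1 = 5, r = 8).**

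| | Stated | Computed |
|---|---|---|
| Early stop, p = 13% | 80% | 79.6% |
| Early stop, p = 5% | 10% | 10.4% |
| Feasible, p = 13% | 4% | 3.7% |
| Feasible, p = 5% | 83% | 82.9% |

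All four agree after rounding. This settles two points of reading: the counts are counts at which accrual stops, and early termination means crossing the first-stage boundary.

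**Step 2: the 40 Gy rule as written (r1 = 6, r = 9).** At p = 7% the feasible probability is built up as follows.

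| x | P(X1 = x) | P(X2 ≤ 8 − x) | Product |
|---|---|---|---|
| 0 | 0.0266 | 0.9927 | 0.0264 |
| 1 | 0.0999 | 0.9780 | 0.0977 |
| 2 | 0.1843 | 0.9417 | 0.1735 |
| 3 | 0.2219 | 0.8650 | 0.1920 |
| 4 | 0.1963 | 0.7290 | 0.1431 |
| 5 | 0.1359 | 0.5327 | 0.0724 |
| Sum | | | 0.7051 |

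The first-stage stop probability is P(X1 ≥ 6) = 0.1350 at p = 7% and 0.7806 at p = 15%. The same sum at p = 15% gives 0.0250. A simulation of 2 million trials agrees (0.7807 and 0.0251 at 15%; 0.1349 and 0.7051 at 7%).

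**Step 3: find the rule that does give the stated figures.** First-stage counts 5 to 9 were crossed with totals 8 to 12. Only 7 and 10 match all four.

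| 40 Gy | Stated | Written rule, 6 and 9 | Rule 7 and 10 |
|---|---|---|---|
| Early stop, p = 15% | 64% | 78.1% | 63.9% |
| Early stop, p = 7% | 6% | 13.5% | 5.8% |
| Feasible, p = 15% | 5% | 2.5% | 5.2% |
| Feasible, p = 7% | 82% | 70.5% | 82.5% |

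Changing one count alone does not help. With 6 and 10, early stopping at 15% is still 78.1%; with 7 and 9, the feasible probability at 7% is 72.9%.

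**Step 4: rule out an approximation as the cause.** For P(X1 ≥ 6) at 15% and 7%, the Poisson approximation gives 75.9% and 14.2%. The normal approximation gives 78.6% and 13.4% with continuity correction, and 72.4% and 8.3% without. None gives 64% and 6%.

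**Step 5: size.** At p = 7%, rejection is 1 − 0.7051 = 29.5%, against a stated 100 − 82 = 18%. Early stopping is 13.5 / 6 = 2.25 times the stated rate. Every outcome that passes under 6 and 9 also passes under 7 and 10, so at p = 7% the two rules reach opposite verdicts in 0.8247 − 0.7051 = 12.0% of trials.

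**The case against.** The arithmetic is not in dispute. The case on the other side concerns consequence and remedy.

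- **The rule itself is clear.** Both statements of it give the same counts, so anyone applying it reaches the same decision whatever the percentages say. This stands. What is wrong is either the description of the rule's performance or the counts, and the text does not show which.
- **The error is conservative.** A dose with a 15% rate passes 2.5% of the time, not 5%. This stands: no hidden risk to patients follows. The cost is a higher chance of rejecting an acceptable dose.
- **It is not the only 40 Gy criterion.** The enlarged cohort has its own primary endpoint, fat necrosis requiring surgery within 3 years, with more than 9 of 180 as the limit. Its stated probabilities reproduce (0.046 and 0.967 against 0.05 and 0.97). This stands and narrows the point to the one-year rule. Section 10.0 nevertheless keeps that rule in force, and Section 2.1 still lists the one-year outcomes.
- **Early termination is nominal.** Accrual does not pause, events can take a year to appear, and 40 to 50 patients enter per year. Neither 6% nor 13.5% is therefore the real chance of halting accrual in time. This stands for the early-stop figures but does not touch the 70.5%.
- **Accrual is over.** The revision history records permanent closure in 2010, with analysis on 330 patients. This stands: a correction now bears on how the 40 Gy result is judged and reported, not on who is enrolled.

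**Conclusion.** The concern holds. The four operating characteristics stated for 40 Gy do not belong to the stopping counts stated for 40 Gy. For the written counts, early termination is 78.1% and 13.5% (stated 64% and 6%), and the chance of being deemed feasible is 2.5% and 70.5% (stated 5% and 82%). Power is overstated by 82 − 70.5 = 11.5 percentage points.

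The result assumes independent bad events with a common rate, 100 evaluable patients in stages of 50, and one-year outcomes known for all. These are the assumptions under which the plan's figures at 32 and 36 Gy reproduce. The stated 40 Gy figures fit counts one higher at each stage. That suggests the largest acceptable counts may have been written as stopping counts, but the document does not establish it. Among the current dose levels only the third is affected.

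**What to change.** Make the counts and the percentages agree in Section 10.0, and record from the design files which of the two was intended. The documents do not decide this, and this review does not.

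- **If 6 and 9 were intended:** keep both statements of the rule and restate the figures as 78% and 13.5% for early termination (true rates 15% and 7%) and 2.5% and 70.5% for being deemed feasible. This changes the sentences giving the 40 Gy probabilities and costs only a less favourable stated power.
- **If the stated percentages were intended:** the counts conflict with them in both places where the rule appears, and both would have to be reconciled. Because outcome data already exist, such a change needs documentary evidence that predates them.

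Until this is settled, any report of the one-year 40 Gy result should give the rule actually applied with the operating characteristics of that rule, and should not cite 82% power for the 6 and 9 counts. No new data are needed.
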